Probiotics are defined as live microbial organisms that when administered in sufficient amounts, can provide a protective benefit to the host (Hojsak, 2017). Use of probiotics in a pediatric population exposed to antibiotics and gastrointestinal surgery such as an appendectomy may provide a protective effect and prevent ADD (Alper, Zangwill, LaRue & Manheimer, 2017; Hayes & Vargas, 2016). In a meta-analysis of randomized controlled trials in pediatrics, literature found that treatment with *Lactobacillus rhamnosus GG* (LGG) reduced in risk of ADD from 23% to 9.6% (RR, 0.48; 95% Cl, 0.26 to 0.89) (Szajewska & Kolodziej, 2015). Studies indicate it is suggested to administer LGG simultaneously with the initiation of antibiotic therapy, before the modification of gut microbiota and overgrowth of pathogens (Szajewska & Kolodziej, 2015).

Lactobacillus rhanmosus GG(LGG®)(Culturelle) is an over the counter dietary supplement that can help to restore the balance in the gut by promoting colonization to support better digestion and immune health. As such, this dietary supplement is not reviewed and approved by the FDA. This study does not intend to investigate route of administration, dose, patient population, or other factor that significantly increases the risk (or decreases the acceptability of the risk) associated with the use of the dietary supplement.

At Children's Medical Center, we see over 1000 cases of appendicitis a year with approximately 1/3 of those patients being complicated appendicitis. Our current treatment at Children's Medical Center for

complicated appendicitis follows two pathways: 1) drainage and deferred appendectomy approximately 6 to 8 weeks later or 2) immediate appendectomy. All children are typically admitted to the hospital for 3 to 5 days, receive a course of IV antibiotics while in hospital and are discharged with oral antibiotics to complete their treatment. There has been an increase in the number of patients receiving prescribed probiotics after surgery.

We propose to perform a randomized controlled trial where one group of patients receive probiotic therapy and another group of patients does not.

We hypothesize patients given probiotics after a diagnosis of complicated appendicitis with immediate appendectomy who receive antibiotic treatment during their inpatient stay will decrease the overall length of stay (LOS) by 25% vs the LOS in those patients who do not receive probiotics.

3. Concise Summary of Project:

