Those who are in agreeance will be consented for the study following all IRB procedures. Randomization will be used to allocate patients into treatment and control group. The treatment group includes 120 patients who have immediate appendectomy and will receive probiotics. The control group includes 120 patients who have an immediate appendectomy and will receive a placebo. Patients in the treatment group will receive a standard dose of Lactobacillus rhamnosus GG capsule twice a day until discharge. The control group will receive a placebo until discharge. If the patient is unable to swallow the probiotic capsule or placebo, the capsule can be opened and sprinkled with food. Current antibiotic standard of care for complicated appendicitis patients includes: ceftriaxone RTA 50mg/kg dose every 24 hours x 7 days and metronidazole RTA 30mg/kg dose every 24 hours x7 days. In patients with a sensitivity to ceftriaxone, metronidazole RTA 30mg/kg dose every 24 hours x7 days and ciprofloxacin 10-15 mg/kg every 8 hours x 7 days will be administered.

Treating medical team and patients/family will be blinded to whether patient is on probiotic or placebo.

[figure not shown]
Data will be collected as stated in section titled, "Concise Summary of Project."

5. Criteria for Inclusion of Subjects:

- Patients with a post-operative diagnosis of complicated appendicitis who undergo an immediate appendectomy.
- Patients between the ages of 4 and 18 years of age.

6. Criteria for Exclusion of Subjects:

- Patients diagnosed with a complicated appendicitis with deferred appendectomy or nonperforated appendicitis
- Patients that have a history of being immunosuppressed, on immunosuppression therapy, or long-term steroid therapy within the last month.
- Patients that have central line access.
- Patients under 4 years of age.
- Patients that are developmentally delayed and cannot ambulate at baseline. •
- Patients with significant past medical history.
- Patients that are in Child Protective Services custody. •
- Patients that are incarcerated.
- Patients that are pregnant. •
- Patients that speak languages other than English and Spanish.

Study Procedures

7. Sources of Research Material:

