All participants will be patients under the care of the General Surgery Department. Information from the Children's Medical Center EHR will be reviewed. Data on outcomes such as length of stay, presence or absence of diarrhea, ambulation/activity level, abdominal pain, surgical history, medications, emergency department visits, readmission rates and stool counts will be extracted from medical records. Standard demographic data will also be obtained.

8. Recruitment Methods and Consenting Process:

After confirmed complicated appendicitis diagnosis, patients and families will be approached by the study team to participate in the study. If families agree to participate, written consent will be obtained, and the patient will be randomized to a study group.

9. Potential Risks:

Inadvertent disclosure of personal medical information. Special precautions are mentioned below in the paragraph *Procedures to Maintain Confidentiality*.

There are potential risks for patients taking probiotics. There have been reported accounts of sepsis in immunosuppressed patients receiving probiotics. Our study will exclude patients with a history of being immunosuppressed, on immunosuppression therapy, or long-term steroid therapy within the last month.

There is a potential risk of psychological stress. Some of the questions we will ask may make the patient/legal guardians feel uncomfortable.

10. Subject Safety and Data Monitoring:

All data will be stored on a password protected computer approved by UTSW and CMC. Access to study data will be restricted to authorized study personnel only.

All data will be stored on a password protected computer in a RedCap system approved by UTSW and CMC. Access to study data will be restricted to authorized study personnel only.

The Principal Investigators and faculty sponsor will review all patient outcomes on a monthly basis. All adverse events, expected and unexpected will be reviewed within 24 hours by the study team and reported to the DSMB and the IRB as per policy.

11. Procedures to Maintain Confidentiality:

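### The plan compares probiotic with no probiotic, but neither the exclusions nor the visible procedures keep non-study probiotics out of the placebo arm before discharge

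*Combined protocol and SAP*

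**What the plan says.** **Intended contrast.** The Background proposes a trial in which "one group of patients receive probiotic therapy and another group of patients does not". Its hypothesis is a 25% shorter LOS than in children who get no probiotic.

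**Setting.** The Background describes the product in these terms: it "is an over the counter dietary supplement that can help to restore the balance in the gut". It says that children at this site "are discharged with oral antibiotics to complete their treatment", and the next sentence reads: "There has been an increase in the number of patients receiving prescribed probiotics after surgery". It gives no rate, product or time point for that prescribing.

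**Procedures.** Section 4 (Methods) has families approached on the inpatient floor after surgery. On the comparator it says: "The control group will receive a placebo until discharge". On blinding: "Treating medical team and patients/family will be blinded to whether patient is on probiotic or placebo". The visible text of Section 4 says nothing about probiotics other than the study product.

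**Eligibility.** Section 6 lists ten exclusions. None concerns probiotic use.

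**Data and analysis.** Section 7 states that "medications, emergency department visits, readmission rates and stool counts will be extracted from medical records". Section 14 plans a Wilcoxon rank sum test for LOS and for the number of diarrheas. It does not say how non-study probiotic use would be reported. Section 13 makes no allowance for such use.

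**The concern.** The control group is defined by not receiving a probiotic, so a probiotic given to a placebo child departs from the design. Two routes are open in the text as written:

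- A child already taking a probiotic at enrolment is eligible.
- After randomization, a clinician can order an open-label probiotic, or a family can bring one in, without breaking any visible rule.

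Blinding does not close the second route. It means only that the order is written without knowledge of the arm. In a child on the active capsule the extra product probably changes little; in a placebo child it removes some or all of the contrast.

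The stake is a missed effect, not a false one. If the probiotic works, exposure in the placebo arm shrinks the observed difference in LOS and in diarrhea. A null result would then be hard to read: the product may not work, or the controls may also have had it. Later analysis can count prescribed use but cannot restore the lost contrast, and product supplied by families may not reach the record.

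**Working it through.** **Inputs from the plan (Section 13).** Control mean LOS 114 h, SD 75.6 h, probiotic LOS 75% of control, 120 per arm, stated power 83%. The difference is 0.25 × 114 = 28.5 h.

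**Assumptions of this check.** Two-sided alpha 0.05 (the plan states none); c, the share of placebo children exposed before discharge; e, the fraction of the full effect that they receive; and the shape of the LOS distribution. The plan gives none of these.

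**Step 1: reproduce the plan's figure.** The standard error is 75.6 × √(2/120) = 9.76 h, and 28.5/9.76 = 2.92. The normal approximation gives Φ(2.92 − 1.96) = 83.2%; the noncentral t gives 82.9%. The stated 83% is therefore right as a t-test on the plan's inputs with no exposure.

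**Step 2: dilute the difference.** With exposure the expected difference is 28.5 × (1 − c·e). At full effect (e = 1), t-test power is:

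| c | Difference (h) | Power |
|---|---|---|
| 0 | 28.5 | 82.9% |
| 10% | 25.65 | 74.5% |
| 20% | 22.8 | 64.3% |
| 30% | 19.95 | 53.0% |

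**Step 3: use the planned test.** Section 14 specifies Wilcoxon, so this is the relevant calculation. LOS was simulated with mean 114 h and coefficient of variation 75.6/114 = 0.663. For the lognormal, the log-scale SD is √ln(1 + 0.663²) = 0.604; for the gamma, the shape is 1/0.663² = 2.27. Probiotic LOS was multiplied by 0.75, and exposed placebo LOS by (1 − 0.25e). With 60,000 simulated trials per cell, power was:

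| c | Lognormal, e = 1 | Lognormal, e = 0.5 | Gamma, e = 1 | Gamma, e = 0.5 |
|---|---|---|---|---|
| 0 | 95% | 95% | 87% | 87% |
| 10% | 90% | 93% | 79% | 84% |
| 20% | 82% | 90% | 69% | 80% |
| 30% | 70% | 87% | 57% | 76% |

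With no exposure the Wilcoxon test has more power than the stated 83%, because these models are skewed and the effect is proportional, so the spread in the probiotic arm shrinks with its mean.

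**Step 4: how much exposure can be absorbed.** Wilcoxon power drops below 80% at about 21% exposed (lognormal, full effect), 47% (lognormal, half effect), 9% (gamma, full effect) or 19% (gamma, half effect).

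**The case against.** **The prescribing may be at discharge.** The sentence follows directly on one about discharge with oral antibiotics. Prescribing that starts at discharge cannot change an index LOS that has already ended. This stands: the text cannot be taken as evidence of inpatient use. It does not settle the point, because the wording is after surgery, not at discharge, and because it leaves prior use and family-supplied product open.

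**Families may already be told.** The consent pages and one figure in Section 4 were not available in the text reviewed, and either could carry such an instruction. This also stands, so absence is weakly supported for families. It is better supported for eligibility, since the exclusion list in Section 6 appears complete.

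**The design discourages extra probiotics.** Every child receives a blinded capsule, and the consent is in the medical record. A clinician who ordered a probiotic would knowingly duplicate the study product in about half of the children. That lowers the risk but forbids nothing. Section 7 medication data would show prescribed use, but only afterwards.

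**The loss may be small.** The Background advises starting the product together with antibiotics, so later use might have less than full effect. At a quarter of the effect and 20% exposure, Wilcoxon power is about 92% (lognormal) or 84% (gamma), both above the stated 83%. Correct: a material loss needs substantial exposure with an effect near full, or a less favorable LOS shape.

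**A stronger reading to resist.** A reader might infer that the placebo arm is in fact receiving probiotics at this site, or that the 83% is wrong. The documents support neither: they give no inpatient rate, and the 83% reproduces.

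**Conclusion.** The concern holds as a gap in enforcement, and it is minor. The plan defines control as no probiotic, yet Section 6 and the visible Section 4 text would admit a child already on one and would permit open-label use until discharge. The direction of any bias is clear: toward no effect on LOS and diarrhea, provided that the probiotic works as hypothesized.

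The size is unknown. The Step 3 figures are a range over assumed exposure, effect and LOS shape, not an estimate. Across 10% to 30% exposure and half to full effect, the loss of Wilcoxon power runs from 2 to 25 percentage points with lognormal LOS (95% to 93% or 70%) and from 3 to 30 points with gamma LOS (87% to 84% or 57%). At the low end this matters little. The case for acting is that exposure cannot be undone after the event, while preventing it costs almost nothing.

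**What to change.** - **Section 6:** add the exclusion *Patients taking a probiotic at enrolment*, checked by one question to the family at consent.
- **Section 4:** add *Non-study probiotics are not to be ordered or given from randomization to discharge in either arm; any clinically necessary exception is recorded.* If the consent form does not already say this to families, add it there.
- **Section 14:** tabulate non-study probiotic use by arm from the medication data already collected, and keep all children as randomized in the main analysis. Treat any analysis by exposure as descriptive, because a probiotic may be started in response to diarrhea.

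Cost: a short amendment, one question, one instruction and one table. The downsides are the loss of a few otherwise eligible children and a limit on clinician discretion during a stay that the Background puts at typically 3 to 5 days.

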Upon IRB approval, patients admitted to the pediatric surgery service with complicated appendicitis who undergo an immediate appendectomy will be approached about participation in the study. Once written consent has been obtained, patients will be randomized into one of two potential study groups. Those randomized to the treatment group will be given probiotic therapy until discharge, while those randomized to the placebo group will be given a placebo until discharge. Data will be collected from the Electronic Health Record (EHR) at Children's Medical Center will include MRN, standard demographics, length of stay, presence or absence of diarrhea, ambulation/activity level, abdominal pain, stool counts, surgical history, medications, emergency department visits and readmission rates. Data will be stored in a CMC/UTSW secured RedCap with access only granted to study team members.

4. Study Procedures:

Design. Prospective Randomized Controlled Trial

Sample.

Data will be obtained from the electronic health record (EHR) from a convenience sample of patients in a single-center pediatric inpatient surgery unit with a diagnosis of complicated appendicitis that undergoes an immediate appendectomy.

Patients will be randomized into two study groups using randomization and utilizing a sealed envelope randomization plan. 120 envelopes will be sealed with a standard sized document marked "probiotic treatment" and 120 envelopes will be sealed with a standard sized document marked "placebo". 240 envelopes will be thoroughly shuffled then labeled sequentially from 1-240 in pen. Envelopes will be placed in a plastic container in numerical order ready for use. One group of 120 patients will be given probiotic therapy until discharge and the other group of 120 patients will be given a placebo until discharge

Methods:

After the appendectomy, patients who meet the inclusion criteria and none of the exclusion criteria will be approached by the study team and offered participation for this study. Patients and families will be approached after their surgery on the inpatient floor. A member of the research team will provide families information about the study in their preferred language (English/Spanish). Aconsent will be signed and scanned into to the patient's medical record.

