All patient information and case report forms will be kept in a locked office with limited access. All computer files will be password protected, encrypted and stored on a secure server. Access will be limited to study team members only. Data will be collected and stored in a secured CMC server in RedCap. The case report includes a unique subject number. The data will be collected, analyzed, and archived following strict confidentiality guidelines. The Investigator will consider all information, results, discoveries, records accumulated, records acquired, or deductions in the course of the study as confidential; other than that information to be disclosed by law.

12. Potential Benefits:

There may be benefit to those patients who receive a probiotic during their course of treatment in a reduction of the incidence of AAD. Future patients may benefit if the protocol proven to be effective in decreasing the incidence of AAD.

13. Sample size calculation

Based on the patient population in Children's Medical Center Dallas, the mean and standard deviation of LOS is 114 and 75.6 hours, respectively. The LOS in the probiotic group is expected to be 75% of the control group. With 120 patients in each group, we have 83% of power to detect statistically significant difference in LOS between the probiotic group and control group.

14. Biostatistics

Descriptive analyses of the continuous and categorical data were performed using means, confidence intervals, proportions and frequencies. Wilcoxon Rank Sum test will be used to compare the LOS, as well as the number of diarrheas, between the treatment group and control group. To investigate which type of patients benefits the most from the treatment, regression analysis will be used to model log-transformed LOS. The independent variable will be treatment type and prognostic factors. The statistical analyses were performed with SAS 9.4.

References:

- Alper, B. S., Zangwill, M., LaRue, J., & Manheimer, E. W. (2017). Point of care application of: 'Probiotics for the prevention of pediatric antibiotic-associated diarrhea' (Cochrane review). *European Journal of Integrative Medicine, 12*: 129-130. https://doi.org/10.1016/j.eujim.2017.06.001

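### Does the missing start, end and readmission rule for length of stay leave the trial's powered endpoint open?

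*Combined protocol and SAP*

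**What the plan says.** The hypothesis in the Background is that probiotic treatment "will decrease the overall length of stay (LOS) by 25" per cent. Section 13 builds the sample size on it: "the mean and standard deviation of LOS is 114 and 75.6 hours, respectively", and "The LOS in the probiotic group is expected to be 75% of the control group", with 120 patients per group and 83% power. Section 14 names the test: "Wilcoxon Rank Sum test will be used to compare the LOS".

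None of these places, nor the data lists in Sections 3 and 7, names the time stamps that open and close the stay. Discharge appears in Sections 3 and 4 as the end of study treatment, not as the end of LOS. Enrolment comes after the operation: Section 4 says "Patients and families will be approached after their surgery on the inpatient floor". Section 3 lists "emergency department visits and readmission rates" as items separate from LOS, with no follow-up window.

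Two further sentences bear on who might see results. Section 4 states "Treating medical team and patients/family will be blinded to whether patient is on probiotic or placebo", and Section 10 states "The Principal Investigators and faculty sponsor will review all patient outcomes on a monthly basis". The figure in Section 4 is not shown in the text available, so it could not be checked for a definition.

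**The concern.** A sole powered endpoint without a written clock normally deserves a query. Patients are randomized after surgery, so some inpatient hours always precede treatment and cannot respond to it. LOS from admission, from end of surgery and from randomization are therefore different numbers. The word *overall* could be stretched to include readmission hours. The planning mean and SD are given without a clock, so a reader cannot prove that they measure the same quantity as the trial endpoint.

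The stake would be freedom to choose. The investigators review outcomes monthly, and the blinding sentence does not mention them. If someone saw results by arm and then reported the most favourable of three readings (admission clock, randomization clock, admission clock plus readmission hours), the false-positive rate would exceed 5%. With assumed pre-dose times of 6 to 24 h and 5 to 15% of patients readmitted for a mean of 96 h, simulation puts it at 6.6 to 8.3%.

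**Working it through.** **1. The plan's own figure.** Inputs from Section 13: control mean 114 h, SD 75.6 h, ratio 0.75, 120 per arm. Alpha is not stated; two-sided 0.05 is assumed.

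- Difference: 0.25 × 114 = 28.5 h.
- Standard error: 75.6 × √(2/120) = 9.76 h.
- Power: Φ(28.5/9.76 − 1.96) = Φ(0.96) = 0.8315. The noncentral t version gives 0.8285.
- For the Wilcoxon test with normal data, scaling n by 3/π gives 0.811 to 0.814, and simulation gives 0.816. With lognormal data of the same mean and SD, simulated power is about 0.95.

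The stated 83% stands.

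**2. What the text implies about the clock.**

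- The planning figures come from the centre's own past patients, who had no trial randomization and no study dose. Those two clocks cannot lie behind 114 h.
- 114/24 = 4.75 days. The Background says these children typically stay 3 to 5 days. The two agree if LOS is the hospital stay in its usual sense.
- The hypothesis concerns antibiotic treatment during one inpatient stay. Readmission is collected as a rate; readmission hours are not mentioned.

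Emergency department arrival or surgery as the start is not strictly excluded, but index admission to discharge is the plain reading.

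**3. Does the start clock matter to the test?** Write admission-clock LOS as pre-dose hours plus post-dose hours. Pre-dose hours are settled before treatment starts, so randomization balances them in expectation and the difference in means is the same on either clock. If they were constant, every rank would be unchanged and the Wilcoxon result identical. If they vary, they add only noise.

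Simulated Wilcoxon power follows (20,000 trials per setting, 120 per arm, 25% cut in post-dose stay). Assumptions: lognormal post-dose stay with mean 114 − h, scaled to a total SD of 75.6 h, and independent lognormal pre-dose time with mean h and SD h/2.

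| Assumed mean pre-dose hours h | Admission clock | Randomization clock |
|---|---|---|
| 6 | 0.933 | 0.935 |
| 12 | 0.895 | 0.903 |
| 24 | 0.816 | 0.849 |

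The gap is 0.2 to 3.3 points, and the two clocks reach different conclusions in about 1 to 7% of simulated trials. With no effect, each clock rejects about 5%. Always taking the better of the two start clocks rejects 5.4 to 6.4%.

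**4. Where the larger numbers come from.** Adding readmission hours (mean 96 h, SD 48 h, equal rates in both arms) to the admission clock gives:

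- h = 6, 5% readmitted: 0.907, a loss of 0.933 − 0.907 = 2.6 points.
- h = 12, 10% readmitted: 0.829, a loss of 6.6 points.
- h = 24, 15% readmitted: 0.684, a loss of 13.2 points.

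These losses belong wholly to an endpoint that the protocol does not propose. The pre-dose hours, readmission rates and readmission durations are all assumptions; the documents give none of them.

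**The case for a change.** The strongest contrary case is that a powered endpoint should not depend on inference. *Overall* is undefined, discharge is tied to treatment rather than to LOS, one sentence would settle the matter, and nothing written stops the people who will define LOS from seeing results first. It can be added that hours before randomization dilute the effect. A 28.5 h saving is 28.5/(114 − h) of the post-dose stay, which is 26.4%, 27.9% or 31.7% for h = 6, 12 or 24. If instead only post-dose hours fell by 25%, with the SD held at 75.6 h, the normal approximation gives 79%, 74% and 64% power.

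It is true that the definition is not written and that the match with the historical figures is not formally confirmed. The rest does not carry. The dilution figures concern how large an effect is plausible, not which clock is used: the plan states its target as 25% of overall LOS, and pre-dose hours cancel from the mean difference on either clock. They also depend on the distribution; the lognormal Wilcoxon results above are higher at every h. The route to false positives needs review by arm followed by a selective choice. Section 10 places the monthly review under safety and data monitoring and does not say that it is by arm. Section 4 is silent on the investigators' blinding and does not say that they are unblinded. The 6.6 to 8.3% is therefore a worst case under assumed conduct, and it includes the reading that the text supports least.

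**Conclusion.** The concern does not call for a change. It identifies a missing detail that analysts would fill sensibly: index admission to index discharge, with readmissions tabulated separately. On that reading the Wilcoxon comparison is unbiased with about 5% type I error, and the 83% power reproduces. The remaining uncertainty over the start point is worth roughly 0 to 3 power points if mean pre-dose time is 6 to 24 h. Any other single clock would be equally valid, so no better primary method is being forgone. Extra sensitivity analyses would be a preference, and one that counts readmission hours would introduce an endpoint the protocol does not propose.

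This rests on three things: two-sided 0.05 is intended, the historical LOS is the ordinary hospital stay (as the 4.75-day mean suggests), and no definition is selected after outcomes are seen by arm. Nothing in the documents contradicts these.

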Title: Probiotics and antibiotic associated diarrhea in pediatric complicated appendicitis: Prospective Controlled-Comparison Trial

NCT NCT04529980

December 15, 2020

The University of Texas Southwestern Medical Center at Dallas Institutional Review Board

Protocol Template (for Investigator Initiated Studies)

Title: Probiotics and antibiotic associated diarrhea in pediatric complicated appendicitis: Prospective Controlled-Comparison Trial

Principal Investigators:

[name], DNP, APRN, PCNS-BC [name], MSN, RN, CPN

Faculty Sponsor: [name]

Purpose: To determine the effectiveness of the use of probiotics in patients with a diagnosis of complicated appendicitis on antibiotic associated diarrhea (AAD).

Background:

Appendicitis is the most common urgent surgical procedure performed on children. Approximately one third of the population end up having complicated appendicitis with evidence of peritoneal contamination and infection or abscess requiring the use of IV antibiotics and prolonged hospital stay. Antibiotic Associated Diarrhea (AAD) is a common complication seen in both outpatient and inpatient settings in approximately a third of all patients treated with antibiotics (Mantegazza, et al., 2018). In particular, pediatric patients experience ADD 11-62% of the time and can up upwards to 80% in hospitalized toddlers (Mantegazza, et al., 2018). Current literature defines AAD as three or more liquid stools per day. The causes of AAD are often related to the use of multiple antibiotics, prolonged hospital stay and gastrointestinal surgery. Antibiotics often disturb the normal enteric microbiome in the gut and allow for an increased growth of pathogens (Hojsak, 2017). AAD can occur as late as six to eight weeks after antibiotic exposure.

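### Does the 83% power fail because the 25% cut in length of stay has no source and exceeds what the cited diarrhea effect could produce?

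*Combined protocol and SAP*

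**What the plan says.** Section 13 (Sample size calculation) takes its baseline from the hospital's own patients: "the mean and standard deviation of LOS is 114 and 75.6 hours, respectively". It then states "The LOS in the probiotic group is expected to be 75% of the control group" and concludes "With 120 patients in each group, we have 83% of power to detect statistically significant difference in LOS". The Background gives the same 25% as the study hypothesis, without a citation. Section 13 does not state alpha, sidedness or the test behind the figure. Section 14 (Biostatistics) names the Wilcoxon rank sum test for LOS and for the number of diarrheas.

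The Purpose concerns a different outcome: "To determine the effectiveness of the use of probiotics in patients with a diagnosis of complicated appendicitis on antibiotic associated diarrhea (AAD". On AAD, the Background cites a meta-analysis in which the probiotic "reduced in risk of ADD from 23% to 9.6% (RR, 0.48", 95% CI 0.26 to 0.89). It gives incidence as "approximately a third of all patients treated with antibiotics" and adds that "pediatric patients experience ADD 11-62% of the time".

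**The concern.** The mean and SD come from local data, but the effect size is only asserted. The documents cite no LOS effect of probiotics and do not say how much AAD lengthens a stay. The Purpose and Section 12 (Potential Benefits) both speak of AAD, so a reader naturally supposes that LOS would shorten because fewer children have diarrhea. On that reading, the cited AAD effect looks far too small to yield 28.5 h per patient.

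LOS is the only outcome with a power statement. If the true LOS effect were much smaller than 25%, the LOS comparison would probably be null, and that might be read as the probiotic not working even if AAD had fallen as the meta-analysis suggests.

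**Working it through.** **The plan's own figure.** Inputs from Section 13: mean 114 h, SD 75.6 h, 120 per arm, ratio 0.75. Two-sided 5% is assumed.

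- Difference: 0.25 × 114 = 28.5 h. Standardized: 28.5/75.6 = 0.377.
- Standard error: 75.6 × √(2/120) = 9.76 h. Power: Φ(28.5/9.76 − 1.96) = Φ(0.96) = 83.2%. The t-test version gives 82.9%.
- One-sided 5% would give 89.9%, so the stated 83% points to a two-sided 5% comparison of means.
- Planned Wilcoxon test: about 81% for a 28.5 h shift in normal data. For a proportional 25% cut in skewed data with the same mean and SD, simulation gives 88% (gamma) and 95% (log-normal).

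**What the AAD route would require.** Assume that LOS falls only through AAD. Hours needed per prevented case = 28.5 / (control risk − probiotic risk). If AAD adds the same mean hours to every case, the SD from the AAD/no-AAD split alone is √(p(1−p)) × hours, where p is the control risk.

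| Control risk and effect | Risk difference | Hours per prevented case | SD from the split |
|---|---|---|---|
| 23% to 9.6% | 0.134 | 213 | 89.5 h |
| One third, RR 0.48 | 0.173 | 164 | 77.5 h |
| 62%, RR 0.48 | 0.322 | 88 | 42.9 h |
| 62%, RR 0.26 | 0.459 | 62 | not computed |

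The first two rows exceed the total SD of 75.6 h. At 23% to 9.6%, that SD would cap the LOS fall at (75.6/0.4208) × 0.134 = 24.1 h, or 21%. The conflict disappears at 62% incidence. It also disappears at 23% to 9.6% if only the prevented cases were prolonged: √(0.134 × 0.866) × 212.7 = 72.5 h.

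**Power under the AAD route.** The documents give no hours per AAD case, so 24, 48 and 72 h are assumptions. Simulated Wilcoxon power, gamma to log-normal:

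- 23% to 9.6%: 7–8%, 12–14%, 18–22%.
- One third, RR 0.48: 8–10%, 17–21%, 30–35%.
- 62%, RR 0.48: 17–21%, 51–62%, 81–89%.

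The answer runs from 7% to 89%, depending on two quantities the plan does not supply.

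**AAD as the alternative primary outcome.** Chi-square, two-sided 5%, 120 per arm: 82% for 23% vs 9.6%. That pair has a ratio of 9.6/23 = 0.42, below the cited RR. With RR 0.48, power is 71% at 23% (vs 11.0%), 38% at 11% (vs 5.3%) and 89% at one third (vs 16%).

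**The case for a change.** The strongest case for a change is that the plan calls the 25% expected, which is a claim about what will happen and not a statement of the smallest difference worth finding. AAD is the only route it quantifies. Its own caution that "AAD can occur as late as six to eight weeks after antibiotic exposure" makes matters worse, because diarrhea after discharge cannot lengthen the index stay. Tabulating LOS by AAD status in hospital records would be cheap and need no more patients.

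Part of this stands. The 25% has no stated source, and at 23% to 9.6% it is hard to reach through AAD alone. Power falls quickly for smaller cuts: 65% at 20%, 42% at 15% and 21% at 10% (same formula as above).

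The rest does not carry. Having only one quantified mechanism does not make it the only mechanism. The hypothesis names LOS without a pathway, the Background credits the product with wider digestive and immune effects, and Section 7 lists abdominal pain and ambulation among the outcomes, either of which could bear on discharge. The SD conflict joins a local SD to an AAD rate from other populations and needs equal added hours per case. The proposed tabulation could mislead, because longer stays allow more time for AAD to appear. AAD before discharge has the same weakness as a primary outcome: a shorter stay leaves less time to observe it, and its rate in these patients is unknown.

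**Conclusion.** No change to the plan follows. Section 13 is arithmetically right for the hypothesis it states: 82.9% by t-test, about 81% by Wilcoxon for a normal shift, and 88% to 95% by Wilcoxon for a proportional 25% cut in skewed data. The unsupported 25% is an optimistic planning choice that the documents neither justify nor refute. The 213 h figure depends on LOS falling only through AAD at exactly 23% to 9.6%. At 62% with RR 0.48 it is 88 h, and with RR at its lower confidence limit 62 h.

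Source, alpha and sidedness are missing details. Two-sided 5% can be inferred from the 83%, and Section 14 supplies the test. A restated power would rest on assumed hours per case and would leave the sample size and the analysis as they are. Moving the primary outcome to AAD exchanges one uncertain power for another. The risk of misreading a null LOS result is real but limited: diarrhea is already compared between arms under Section 14, so a reduction could still be seen beside the LOS result.
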